4.2.1.2. Unsolicited AEs

An AE is any untoward medical occurrence in a clinical study participant, temporally associated with the use of a study intervention, whether or not considered related to the study intervention. An AE can therefore be any unfavorable and unintended sign (including an abnormal laboratory finding), symptom, or disease (new or exacerbated) temporally associated with the use of a study intervention.

The verbatim reports of unsolicited AEs will be reviewed by a qualified person and the signs and symptoms will be coded according to the Medical Dictionary for Regulatory Activities (MedDRA) Dictionary for Adverse Reaction Terminology. Every verbatim term will be matched with the appropriate Preferred Term (PT).

A study intervention causally related AE is defined as an AE for which the investigator classifies the possible relationship to study intervention as “Yes”. Investigators will not be required to assess the causality of solicited AEs if the onset is during the solicitation period.

The investigator is obligated to assess the relationship between study intervention and each occurrence of each AE/SAE/device deficiency. The investigator will use clinical judgment to determine the relationship.

The percentage of participants with any unsolicited AEs within the 28-day follow up period (i.e., Day 1-Day 28 post-dosing) with its exact 95% confidence interval (CI) will be tabulated by group and by MedDRA PT and System Organ Class (SOC). Similar tabulation will be done for Grade 3 unsolicited AEs, for any causally related unsolicited AEs, for Grade 3 causally related unsolicited AEs and for unsolicited AEs resulting in a medically attended visit.

In the AE summaries, a participant with 2 or more AEs within the same SOC or PT level but different relationship will be counted only once in the level using the related incident.

4.2.1.3. Adverse Events of Special Interest

The following events are considered as AESIs in this study.

Severe hypersensitivity reactions within 24 hours after study intervention administration

Myocarditis/pericarditis. Refer to Section 8.3.4 of the protocol for myocarditis/pericarditis assessment and definitions.

The summary of event characteristics will be provided for each AESI as well as any potential immune-mediated diseases [pIMDs] (new onsets and exacerbations) including number and percentage of participants with any event. In addition, summary will be provided by relationship to study intervention, maximum grade/severity, outcome, and the action taken. The worst-case approach will be applied at participant level for the maximum grade/severity, i.e., a participant will only be counted once as the worst case from all the events experienced by the participant. For action taken for an event, a participant will be counted once under each action.

The percentage of participants with at least 1 report of SAE (any, related, fatal and fatal related), with at least 1 report of MAE and with at least 1 report of AESI, respectively, classified by the MedDRA SOC and PT and reported from Dose 1 up to study end will be tabulated with exact 95% CI.

In the AESI/SAE summaries, a participant with 2 or more AEs within the same SOC or PT level but different relationship will be counted only once in the level using the related incident.

4.2.1.4. Laboratory Data

Protocol-required Safety Laboratory Tests (Phase 1 only)

The following laboratory assessments will be performed:

Assay type	System	Component	Method
Hematology	Whole Blood	White Blood Cells count and differentials	As per local laboratory procedures
	Whole Blood	Erythrocytes	
	Whole Blood	Hemoglobin	
	Whole Blood	Glycated hemoglobin (Hba1c) *	
	Whole Blood	Platelets	
Biochemistry	Serum	Blood urea nitrogen/Urea	As per local laboratory procedures
		Creatinine	
		Alanine aminotransferase (ALT)	
		Aspartate aminotransferase (AST)	
		Troponin (Troponin I and/or Troponin T)	
Urinalysis* **	Urine	Leukocytes, Blood, Proteins, Glucose, Ketones, Bilirubin, Urobilinogen, Nitrite, Specific gravity, pH	

* Only applicable for screening visit in Phase 1.

** Urinalysis will be done by dipstick.

Individual safety laboratory measurements for hematology, chemistry, and urinalysis laboratory panel will be provided. All listings will include the age group, study group, participants ID, laboratory test name and result, date and time of measurements, reference range, and flag for measurements that are outside the reference range.

Frequency table of normal range status (below, within, above) will be provided for each laboratory assessment/group and visit according to status at baseline.

Any clinically relevant laboratory results will be identified using a flag and these will be reported as AE.

A by-participant listing will be provided for pregnancy test.

Refer to the Section 4.2.1 for the analysis of participants reporting a shift from non-clinically significant laboratory value on Day 1 (pre-dose) to clinically significant abnormal laboratory value on Day 8 (post-dose) or on Day 29 (post-dose) for hematology and clinical chemistry. These events will be grouped according to MedDRA Classification.

In addition, frequency table of clinical relevance (Yes/No) will be provided for each laboratory assessment/group and visit according to status at baseline.

4.2.1.5. Analysis of reactogenicity: Bayesian Logistic Regression Model (BLRM)

An adaptive BLM will be used to inform on the posterior probability of the true Grade 3 solicited event rate for all dose levels used in Phase 1 study groups. The use of Bayesian response adaptive models for Phase 1 studies has been advocated by the European Medicines Agency (EMA) adopted guideline on small populations [EMA, 2006] and by Rogatko et al. [Rogatko, 2007] and is one of the key elements of the FDA's Critical Path Initiative.

The modified version of the 2-parameter BLM described by Neuenschwander et al., 2008 [Neuenschwander, 2008] which accounts for the total amount of HA and NA in each mRNA formulation will be used to assess reactogenicity and recommend the mRNA doses to proceed to Phase 2 of the study.

The BLM is specified as follows:

$$\text{logit}(p(f)) = \log(\alpha) + \beta_1 * \log(d_{\text{HA}}/d^*) + \beta_2 * \log(d_{\text{NA}}/d^*)$$

where

- $p(f)$ = percentage of participants with Grade 3 solicited event at mRNA formulation, f
- $\text{logit}(p) = \log(p/(1-p))$
- $d^* = 50 \mu\text{g}$ is the reference dose representing the total mRNA dose
- α is the intercept parameter
- β_1 is a dose effect due to total amount of HA
- β_2 is a dose effect due to total amount of NA

Since no prior information is available, the uncertainty about the dose-tolerance relationship (parameters α and β [i.e., β_1 and β_2]) is expressed by a mixture of 2 bivariate normal distributions as follows:

- 80% weight for minimally informative component: $\log(\alpha) \approx \text{normal}(\text{mean} = -1.516, \text{var} = 1)$ and $\log(\beta) \approx \text{normal}(\text{mean} = -1.553, \text{var} = 1)$, a priori assuming 10% and 18% Grade 3 solicited event rate at 2 μg and 50 μg , respectively.
- 20% weight for toxicity component: $\log(\alpha) \approx \text{normal}(\text{mean} = -0.708, \text{var} = 1)$ and $\log(\beta) \approx \text{normal}(\text{mean} = -1.143, \text{var} = 1)$, a priori assuming 15% and 33% Grade 3 solicited event rate at 2 μg and 50 μg , respectively.

A zero covariance between priors is assumed. The same prior information is assumed for β_1 and β_2 reflecting *a priori* no difference between the same amounts of HA and NA on adverse reaction.

A greater than 50% posterior probability that the Grade 3 solicited event rate $\geq 18\%$ at a given mRNA dose will indicate that the dose may not be tolerable. The result of the BLRM will be available to the SRT and iSRC at each meeting as a recommendation tool for deciding if non-sentinel participants should be enrolled for each dose level and what dose levels to proceed to Phase 2 of the study.

4.2.2. Co-primary and Secondary Immunogenicity Endpoints

At each phase and for OA and YA separately, the group difference between each mRNA group and the control group will be assessed separately as follows for **CCI** [REDACTED]

- At each post-dosing timepoint separately, the 2-sided CI for group GMT ratio between investigational study intervention dose and (over) the control group will be derived from an ANCOVA model on log10 transformed concentration. The ANCOVA model will include group (i.e., each of the investigational study intervention and the control group), actual age of participants, country, flu vaccination history and log10-transformed concentration at pre-dosing as fixed effects. The adjusted GMT and GMI in each group will be obtained from the same model with 95% CI. Missing data will not be replaced. Concentrations below the assay lower level of quantification (LLOQ) will be replaced by half the assay LLOQ.
- For a given age group, the 2-sided 95% CI on group difference in SCR between an investigational study intervention and (minus) the control group will be computed at Day 29 based on the method of Miettinen and Nurminen [Miettinen, 1985].
- CCI** [REDACTED]
[REDACTED]
[REDACTED]

All analyses will be performed separately for each age group, where applicable.

Abbreviation/term	Definition
GMI	The geometric mean of the ratios of the post-dosing titer over the Day 1 titer.
CCI [REDACTED] [REDACTED]	The percentage of dosed participants who have either a CCI [REDACTED] and a post-dosing CCI [REDACTED] or a CCI [REDACTED] and at least a 4-fold increase in post-dosing CCI [REDACTED].
CCI [REDACTED] [REDACTED]	The percentage of dosed participants who have either a CCI [REDACTED] and a post-dosing CCI [REDACTED] or a pre-dose CCI [REDACTED] and at least a 4-fold increase in post-dosing CCI [REDACTED].
CCI [REDACTED] [REDACTED]	The percentage of dosed participants with a CCI [REDACTED]
S+ (seropositive)	Titer \geq LLOQ

The following SAS code will be used for computation of GMT ratio where AVAL and BASE are the \log_{10} transformed GMC values at pre-dose and post-dose respectively, while country and vaccination history are the minimization factors at randomization:

```
PROC GLM DATA=immuno ALPHA=0.05;
  CLASS trt01a country vacchist;
  BY agecat strain;
  MODEL aval = trt01a country vacchist base age;
  LSMEANS trt01a / CL;
RUN;
```

For the purpose of analysis, previous flu vaccination history reported as 'Unknown' will be classified as 'No'.

The SCR will be computed using the following SAS code where AVALC is the seroconversion status post-dose:

```
PROC FREQ DATA=immuno;
  BY agecat strain;
  TABLE trt01a*avalc / RISKDIFF (CL=MN) ALPHA=0.05;
RUN;
```

The assays used in this study and their LLOQs are presented in [Table 3](#).

Table 3 Assay cut-off values for various assays in Phase 1

Assay	Unit	Test ID	LLOQ
CCI			

Table 4 Assay cut-off values for various assays in Phase 2

Assay	Unit	Test ID	LLOQ
CCI			

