2	Refer to 1	To evaluate the humoral immune response induced by the investigational study intervention	
 CCI [REDACTED] at Day 29 (GMT) Fold increase in [REDACTED] from Day 1 to Day 29 (GMI) [REDACTED] from Day 1 to Day 29 (SCR) CCI [REDACTED] at Day 1 and Day 29 (SPR) CCI [REDACTED] at Day 29 (GMT) Fold increase in [REDACTED] from Day 1 to Day 29 (GMI) CCI [REDACTED] from Day 1 to Day 29 (SCR^t) 	
a. Vaccination administration errors.
 
b. Taken prohibited medication or vaccination prior to Day 29 blood draw.
 
c. Medical condition forbidden by protocol (i.e., either a confirmed immunodeficiency condition, new malignancy, or development of confirmed influenza disease) prior to
	
Hypothetical strategy: data from participant after ICE will be excluded from the analysis.
	
 Between-group geometric mean titer (GMT) ratio (Flu mRNA candidate over Comparator) with 95% confidence interval (CI) Within-group geometric mean increase (GMI) with 95% CI Between-group difference in seroconversion rate (SCR³) (Flu mRNA candidate minus Comparator) with 95% CI Between-group difference in seroprotection rate (SPR³) (Flu mRNA candidate

Ref #	Population	Objectives	Variable (Endpoint)	Intercurrent event (ICE) ²		Population level summary
				Description	Handling strategy	
				Day 29 blood draw. d. Blood sample collected for Day 29 out of window		minus Comparator) with 95% CI
Secondary						
2	Refer to 1	To evaluate the humoral immune response induced by the investigational study intervention	
 • CCI at Day 92 and Day 183 (GMT) • Fold increase in CCI CCI from Day 1 to Day 92 (GMI) • Fold increase in CCI CCI from Day 1 to Day 183 (GMI) • CCI CCI at Day 183 (SPRt) • CCI at Day 92 and Day 183 (GMT) • Fold increase in CCI CCI from Day 1 to Day 92 (GMI) Fold increase in CCI CCI from Day 1 to Day 183 (GMI)	Refer to 2	Refer to 2	Refer to 2

Endpoints are designed for all the participants, unless indicated otherwise in the table.

[figure not shown]
AE: adverse event; AESI: adverse event of special interest; CI: confidence interval; GMI: mean geometric increase; GMT: geometric mean titer; CCI CCI ; ICE: intercurrent event; MAE: medically attended event; CCI CCI , SAE: serious adverse event; SCR: seroconversion rate; SPR: seroprotection rate; YOA: years of age.

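### SAP 4.2.2 defines GMI as the participants' own geometric mean fold rise, but takes each group's adjusted GMT and GMI from an ANCOVA whose only code uses default LS-means, with undeclared equal weights for country and vaccination history

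*SAP*

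**What the plan says.** - **Definition.** The table of terms in SAP 4.2.2 gives GMI as "The geometric mean of the ratios of the post-dosing titer over the Day 1 titer". Protocol 9.3.2 has the same definition.
- **Status.** SAP Table 2 (Section 1.1.1) lists "Within-group geometric mean increase (GMI) with 95% CI" as a population-level summary for the co-primary humoral objective. SAP 4.3.1 carries the method over to the secondary endpoints at Days 92 and 183.
- **Source of the per-group values.** SAP 4.2.2 also states: "The adjusted GMT and GMI in each group will be obtained from the same model with 95% CI".
- **Code.** One block of SAS code is given for that model. It is introduced with "The following SAS code will be used for computation of GMT ratio" and contains "CLASS trt01a country vacchist", "MODEL aval = trt01a country vacchist base age" and "LSMEANS trt01a / CL", run by age category and strain. Unknown vaccination history is counted as no vaccination, so that factor has two levels.
- **What is not stated.** The code has no weighting option and no step that turns an LS-mean into a GMI. Section 4.2.2 plans no separate unadjusted GMI. SAP 6.2.1.6 describes GMT as a plain antilog of the mean log value and does not mention adjustment.

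**The concern.** The definition averages over the participants who were analysed. A default LS-mean does not. It gives each of C countries weight 1/C and each vaccination-history level weight 1/2, whatever the enrolment, and sets pre-dose titre and age to their observed means. The result combines an artificial country and history mix with the real baseline mix. A country with 5% of participants counts as much as one with 85%.

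Minimization does not remove this. It keeps the arms alike in country and history, but it does not make countries equal in size or make half the participants previously vaccinated.

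What is at stake is the absolute level and the interval width of the within-group GMT and GMI. These would depend on how many small countries enrolled, and the co-primary GMI would not be the quantity that the SAP defines. Two programmers following the SAP could report different co-primary GMIs.

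**Working it through.** **1. The plan's own figure.** SAP 5.2 gives 108 evaluable per group, SD 0.5 log10 and a 1.36-fold half-width for the GMT ratio. 120 × 0.90 = 108, and 10^(1.96 × 0.5 × √(2/108)) = 10^0.1334 = 1.359. The figure reproduces. It concerns the ratio, which this point leaves untouched. No precision figure is given for GMI.

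**2. Size of the shift.** In the additive model, the expected ratio of the default LS-mean to the observed-margins LS-mean, on the fold scale, is

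F = 10^[ Σ(1/C − s_c)·e_c + (0.5 − v)·e_v ],

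where s_c is a country's share, e_c its log10 effect, v the share previously vaccinated and e_v the log10 effect of vaccination. F contains no group term, so it is the same for every group.

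The documents say only that the study is multi-country. The shares, effects and number of countries (three) below are all assumptions.

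| Shares (%) | Country effects | v | e_v | Exponent | F |
|---|---|---|---|---|---|
| equal | 0/0.15/0.3 | 0.25 | −0.3 | 0 − 0.075 | 0.84 |
| equal | any | 0.50 | any | 0 | 1.00 |
| 70/20/10 | 0/0.1/0.2 | 0.50 | −0.2 | 0.060 + 0 | 1.15 |
| 70/20/10 | 0/0.1/0.2 | 0.75 | −0.2 | 0.060 + 0.050 | 1.29 |
| 85/10/5 | 0/0.15/0.3 | 0.75 | −0.3 | 0.120 + 0.075 | 1.57 |

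**3. Width of the per-group interval.** With four arms of equal size and the same mix, and with country and history independent, the SE of a group's LS-mean is multiplied by

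√{1 + [Σ(1/C)²/s_c + Σ(1/2)²/s_h − 2]/4},

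where s_h is the share in each history level.

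- 70/20/10% with 75% vaccinated: √(1 + (1.825 + 1.333 − 2)/4) = 1.14.
- 85/10/5% with 20% vaccinated: √(1 + (3.464 + 1.563 − 2)/4) = 1.33.

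This depends only on unequal level sizes. No true country or history effect is needed.

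**4. Simulated check.** The SAP's additive model was fitted to simulated data with four arms of 108 and the same country and history mix in each arm, using the 70/20/10%, v = 0.75 row above. Adjusted GMI was taken as 10^(LS-mean − overall mean log10 baseline), because the SAP does not name the baseline to subtract. Defined GMI was 10^(within-group mean of log10 post − log10 pre).

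| Arm | Defined GMI | Default LS-means | Observed margins | Ratio to arm 1, either weighting |
|---|---|---|---|---|
| 1 | 3.01 | 3.99 | 3.04 | 1.000 |
| 2 | 3.23 | 4.22 | 3.21 | 1.056 |
| 3 | 4.83 | 6.01 | 4.57 | 1.505 |
| 4 | 5.57 | 7.70 | 5.86 | 1.928 |

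- Default values are 24% to 38% above the defined GMI. Observed-margins values are within about 5% of it.
- Default divided by observed margins is 1.31 in every arm (for example 3.99/3.04), against the expected 1.29. The difference is sampling error in the fitted effects.
- Ratios between arms are the same under both weightings.
- Per-group half-width is 1.24-fold against 1.21-fold. At 85/10/5% with 20% vaccinated it is 1.29 against 1.21.
- With the same unequal shares but zero true effects, default over observed margins was 3.993/3.925 = 1.02, which is sampling error alone.

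**5. What observed margins do not repair.** Leaving aside age and small differences in mix, the log10 gap between an observed-margins GMI and the defined GMI is (1 − b) × (group baseline mean − overall baseline mean), where b is the baseline slope. With an assumed 0.15 log10 baseline shift in arm 4, the defined GMI was 4.68 and the observed-margins value 5.67, which is 21% too high. The other three arms fell 4% to 10% below their defined values.

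**The case against.** The strongest reply has four parts.

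- **The code is labelled for the GMT ratio.** This is true. A reader might infer that the code shown computes GMI, but it contains no such step. The link comes from the separate sentence that takes adjusted GMT and GMI from the same model. It still matters, because LS-means are the only estimates the code requests and no other derivation is given.
- **An adjusted GMI differs from a raw one by design, and equal weighting is a conventional standardisation.** This also stands. Equal weights are not an error in themselves. The defect is that Section 4.2.2 does not say whether the co-primary GMI is raw or adjusted, declares no weights, and gives a definition that the default output does not meet.
- **The consequence is limited.** This stands. The factor is common to all groups within a stratum, strain and visit. SCR comes from separate code, the study has no formal hypothesis testing, and no GMI threshold appears in the visible text.
- **Observed margins alone would not restore the definition.** This is correct, as step 5 shows, so the remedy has to go further than one option.

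The objection does not dispose of the mismatch itself. A within-group summary has no comparator in which the common factor could cancel.

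**Conclusion.** The mismatch is real: the co-primary within-group GMI is defined one way and, read literally, derived another. The per-group adjusted GMT and GMI carry a factor of about 0.84 to 1.57 over the assumed shares and effects. In expectation the factor is exactly 1 when levels are equally filled or effects are zero. Per-group intervals are wider whenever levels are unequal, by 14% and 33% on the log scale in the two cases worked.

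Three stronger readings are tempting, and the documents support none of them:

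- **That GMI will be inflated.** The factor can fall on either side of 1, and no shares or effects are given that would fix its direction or size.
- **That comparisons with control or between doses are biased.** The model has no group interaction, so GMT ratios and the ranking of groups do not move. SCR differences do not come from this model.
- **That equal weighting explains the whole gap.** Holding pre-dose titre and age at overall means also separates the adjusted GMI from the defined one.

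Severity is minor to moderate. It affects the reported level and precision of a co-primary summary, not the between-group conclusions.

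**What to change.** Amend SAP 4.2.2 as follows.

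1. Report the co-primary within-group GMI directly: the antilog of the within-group mean of log10(post/Day 1), with its 95% CI. This matches the SAP's own definition.
2. For the model-adjusted GMT, and for any adjusted GMI (labelled as such), add the observed-margins option `OM` after `CL` in the LSMEANS statement. State that the margins are those of the participants analysed in that age stratum, and state which baseline mean is subtracted to obtain the adjusted GMI.
3. Record the change in SAP 4.8, because Protocol 9.3.2 also takes the adjusted GMI from the ANCOVA.

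The cost is one SAS option, one extra summary and a sentence or two. No new data are needed and the GMT ratios do not change.

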4.3. Secondary Endpoint(s) Analyses

To evaluate the humoral immune response induced by the investigational study intervention. The CCI for each strain on Day 92 and Day 183 will be assessed as follows:

- CCI at Day 92 and Day 183 (GMT)
- Fold increase in CCI from Day 1 to Day 92 (GMI)
- Fold increase in CCI from Day 1 to Day 183 (GMI)
- CCI at Day 183 (SPR)
- CCI at Day 92 and Day 183 (GMT)
- Fold increase in CCI from Day 1 to Day 92 (GMI)
- Fold increase in CCI from Day 1 to Day 183 (GMI)

4.3.1. Main Analytical Approach

The analyses of secondary endpoints will be performed as described in Section 4.2.2.

[figure not shown]

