## CONFIDENTIAL

217884 (FLU SV mRNA-002)  
Protocol Amendment 2 Final

Type Of Contact	Visit 1	Visit 2*	Contact 1**	Contact 2	Visit 3†	Visit 4	Visit 5‡	Visit 6‡	Notes
Timepoints	Day 1	Day 2	Day 2	Day 3	Day 8	Day 29	Day 92	Day 183	
Recording of SAEs related to study participation, or to a concurrent GSK medication/vaccine	●	●	●	●	●	●	●	●	See Section 8.4.1 for details
Record AEs leading to withdrawal from study	●	●	●	●	●	●	●	●	See Section 8.4.1 for details
Recording of non-serious adverse events	●	●	●	●	●	●			See Section 8.4.1 for details
Recording of MAEs, SAEs, AESIs and pregnancies	●	●	●	●	●	●	●	●	See Section 8.4.1 for details
Record any concomitant medications	●	●	●	●	●	●	●	●	See Section 6.9 for details
Record any intercurrent medical conditions	●	●	●	●	●	●	●	●	See Section 9.2 for details
Study conclusion								●	See Section 10.1.10 for details

● Is used to indicate a study procedure that requires documentation in the individual CRF/eCRF

○ Is used to indicate a study procedure that does not require documentation in the individual CRF/eCRF

† Is used to indicate a study procedure to be performed prior to study intervention administration.

‡ Is used to indicate a study procedure recorded in eDiary.

\* Visit 2 (Day 2) will only be applicable for participants in the exploratory immunogenicity subset in Phase 2. Remaining Phase 2 participants will not have a visit at Day 2.

\*\* Contact 1 (Day 2) will only be applicable for the sentinel OA participants in Phase 2. Remaining Phase 2 participants will not have a contact at Day 2.

\*\*\* Blood samples should only be collected for participants who did not receive a standard of care vaccination against seasonal flu since their enrollment into the study.

† Visit 3 (Day 8) will be replaced by a Contact for all non-subset participants in Phase 2 and if participant did not report any adverse events that would require physical examination on site.

‡ Visit 5 and 6 will be replaced by a Contact if participant has received the standard of care vaccination against seasonal flu after Day 29 and prior to this visit and did not report any adverse events that would require physical examination on site.

Contact may be via telephone, SMS, email, video-telephone/telemedicine or other means, depending on local best practice.

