### 8.2.3. Immunological read-outs

**Table 12** Immunological read-outs

Blood sampling timepoint		Subset name	Approximate No. of participants	Component	
Type of contact and timepoint	Sampling timepoint				
Day 1	Pre-dose	All enrolled participants (Phase 1 and Phase 2)	1272	CCI	
		Participants in exploratory immunogenicity subset (Phase 2)	400		
		For CCI [REDACTED] sample collection will be limited to selected sites.			
			400		
			400		
			400		
			400		
Day 2	Post-dose	Participants in exploratory immunogenicity subset (Phase 2)	400		
Day 8	Post-dose	Participants in exploratory immunogenicity subset (Phase 2)	400	CCI	
			400		
			400		
			400		
			400		
Day 29	Post-dose	All enrolled participants (Phase 1 and Phase 2)	1272		
		Participants in exploratory immunogenicity subset (Phase 2)	400		
		Participants in exploratory immunogenicity subset (Phase 2)	400		
Day 92	Post-dose	All enrolled participants (Phase 1 and Phase 2)	1272 ‡		

Blood sampling timepoint		Subset name	Approximate No. of participants	Component
Type of contact and timepoint	Sampling timepoint			
Day 183	Post-dose	All participants enrolled (Phase 1 and Phase 2)	1272‡	CCI
		Participants in exploratory immunogenicity subset (Phase 2)	400‡ 400‡ 400‡ 400‡	

Ab: antibody; CCI

\* Strains used to design the study intervention

\*\* CCI

‡ Given that samples will only be collected from participants who did not receive a standard of care vaccination against seasonal flu, this number represents the maximum number of participants who will have a sample collected for the Visit.

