3. ANALYSIS SETS

Analysis Set	Definition / Criteria	Analyses Evaluated
Screened	All participants who were screened for eligibility.	Screening failure
Enrolled	All participants who entered the study (who were randomized or received study intervention or underwent a post-screening study procedure). Note: screening failures (who never passed screening, even if rescreened) and participants screened but never enrolled into the study (met eligibility but not needed) are excluded from the Enrolled analysis set as they did not enter the study.	Study population
Exposed Set (ES)	All participants who received a study intervention. Analysis per group is based on the study intervention administered.	Safety, immunogenicity if applicable, demography
Per Protocol Set (PPS)	All eligible participants who received the dose of study intervention as per protocol, had immunogenicity results pre- and Day 29 post-dosing for at least one CCI [REDACTED], without intercurrent conditions (influenza disease, new malignancy and immunocompromised condition) that may interfere with immunogenicity and without prohibited concomitant medication/vaccination before Day 29. The analysis will be done according to the study intervention that participants received. Results from blood sample deviating from the dosing/blood draw intervals (refer to Table 9 and Table 10) as well as results obtained after intercurrent conditions (influenza disease, new malignancy and immunocompromised condition) that may interfere with immunogenicity or after prohibited concomitant medication/vaccination during this period will be excluded from the PPS.	Immunogenicity, demography

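### Day 92 and Day 183 GMTs come from separate complete-case ANCOVAs although late sampling stops by design after flu revaccination; the unused Day 29 titre would give narrower intervals under a weaker missing-data assumption

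*SAP*

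**What the plan says.** SAP 4.3.1 sends the secondary immunogenicity endpoints to SAP 4.2.2: "The analyses of secondary endpoints will be performed as described in Section 4.2.2". There the model is fitted by visit ("At each post-dosing timepoint separately, the 2-sided CI for group GMT ratio"), and the program line is "MODEL aval = trt01a country vacchist base age". The only titre on the right-hand side is the pre-dose one. The same section says "Missing data will not be replaced", and PROC GLM drops any record whose outcome is missing, so each late analysis is complete-case. Protocol 9.3.2 describes the same analysis.

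On sampling, the footnote to protocol Table 2 (repeated under Table 10) reads "Blood samples should only be collected for participants who did not receive a standard of care vaccination against seasonal flu since their enrollment". It applies to Day 92 and Day 183. Protocol Table 12 says of the late counts that "this number represents the maximum number of participants who will have a sample collected for the Visit".

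On the Day 29 titre, SAP Section 3 admits to the per-protocol set (PPS) participants who "had immunogenicity results pre- and Day 29 post-dosing for at least one" assay item, whose name is redacted.

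On the estimand, SAP Table 2 sets a hypothetical strategy for the primary immunogenicity objective, and the secondary row refers back to it. The dated events in that row (prohibited medication or vaccination, forbidden medical condition, out-of-window sample) all relate to the Day 29 draw.

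**The concern.** A participant who takes a seasonal flu vaccine after Day 29 has a pre-dose and normally a Day 29 titre, but no later one. The planned analysis of Day 92 or Day 183 then discards that person entirely, although the Day 29 titre is likely to be the best available predictor of the missing value.

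Two things are at stake. The late intervals are wider than the collected data allow. And a complete-case ANCOVA is unbiased only if being sampled late is unrelated to the late titre given group, age, country, vaccination history and pre-dose titre. A likelihood model that includes Day 29 needs this only after conditioning on the Day 29 titre as well, which is a weaker condition.

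There is also a gap in the text: revaccination after Day 29, the planned cause of late loss, is not listed as an intercurrent event for the secondary estimand.

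**Working it through.** **Inputs from the documents.** 108 evaluable per group, SD 0.5 on the log10 scale, 10% unevaluable (SAP 5.2); 120 enrolled per group (SAP 1.2); 95% two-sided intervals (SAP 4.1.1).

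**Inputs assumed.** The fraction *m* without a late sample, 10% to 50%. The correlation *r* between Day 29 and late log10 titre after adjustment for the model covariates, 0.5 to 0.8. SD 0.5 is carried over to the late visits; this affects the fold values but not the percentage narrowing.

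**Step 1: reproduce the stated precision.** Half-width = 10^(1.96 × 0.5 × √(2/108)) = 10^0.1334 = 1.359, matching the stated 1.36-fold. Also 108/0.90 = 120. The documents give no precision figure for Day 92 or Day 183.

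**Step 2: late precision.** Complete-case half-width = 10^(1.96 × 0.5 × √(2/(108(1−m)))). With Day 29 complete and in a likelihood model, the large-sample variance is multiplied by 1 − r²m, so the log-scale interval narrows by 1 − √(1 − r²m). At m = 0.3 and r = 0.7: 1 − √(1 − 0.49 × 0.3) = 1 − √0.853 = 7.6%.

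| Missing | n per group | Complete-case | Day 29 used, r = 0.5 | r = 0.7 | r = 0.8 |
|---|---|---|---|---|---|
| 10% | 97.2 | 1.382 | 1.377 (1.3%) | 1.371 (2.5%) | 1.368 (3.3%) |
| 30% | 75.6 | 1.443 | 1.423 (3.8%) | 1.404 (7.6%) | 1.391 (10.1%) |
| 50% | 54.0 | 1.544 | 1.501 (6.5%) | 1.458 (13.1%) | 1.431 (17.5%) |

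Entries are fold half-widths of the GMT ratio, with the log-scale narrowing in brackets.

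**Step 3: check by simulation.** 108 per group, 3,000 replicates, SD 0.5, r = 0.5 or 0.8, about 30% to 50% missing. With missingness by group only (31% missing), the ratio of half-widths was 0.96 at r = 0.5 and 0.88 at r = 0.8; the formula gives 0.96 and 0.90. When Day 29 itself drove missingness the gain was smaller (0.94 at 34% missing, r = 0.8, against 0.88 by formula).

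**Step 4: bias under assumed mechanisms.** True GMT ratio 1.5; where titre drives missingness, the log-odds slope is 2 per log10.

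| Late missingness depends on | Complete-case ratio | Ratio using Day 29 |
|---|---|---|
| Pre-dose titre or group only | 1.49–1.51 | 1.49–1.51 |
| Low Day 29 titre, same in both groups | 1.42–1.46 | 1.50–1.51 |
| Low Day 29 titre, one group only | 1.74–2.13 | 1.50–1.52 |
| Low unobserved late titre | 1.40–1.42 | 1.42–1.47 |

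In the second row the complete-case control GMT is inflated 1.19- to 1.50-fold, and using Day 29 restores it to 1.00. In the last row it is inflated 1.42- to 1.67-fold, and using Day 29 reduces this to 1.15- to 1.49-fold.

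**The case against.** The strongest reply is that nothing shows that late loss depends on Day 29 response. Phase 2 is observer-blind (protocol 6.4), and laboratory results that could unblind are withheld from sites (protocol Section 8), so neither participants nor sites should be acting on a measured titre. The obvious drivers of revaccination (age, country, vaccination history) are already covariates. Where missingness follows only pre-dose titre or group, the complete-case ratio is unbiased. This stands, and it makes bias a conditional risk. One route does remain open: results after influenza disease are also removed from the PPS (SAP Section 3), and that loss could plausibly follow antibody response.

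Second, the gain may be modest, because *r* must be the correlation after adjustment. As an illustration with assumed values, a raw correlation of 0.7, with pre-dose titre correlated 0.6 with both visits, leaves (0.7 − 0.36)/(1 − 0.36) = 0.53. At 30% missing the narrowing is then 4.3%. This stands, and the range is stated in terms of the adjusted correlation.

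Third, the study is descriptive (SAP Section 2), the endpoints are secondary, and a repeated-measures model makes its own assumptions. If covariates lacked visit interactions it would be more restrictive than the separate ANCOVAs, and it would yield a second Day 29 estimate. These points shape the fix. SAP 4.4 is redacted, so supporting analyses there cannot be excluded.

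**Conclusion.** The point holds as a cheap improvement. The late analyses leave out a predictor that has already been collected, in a design that plans to lose late samples. If any late samples are missing and the adjusted correlation is not zero, precision is lost: 1.3% to 17.5% of the log-scale interval width over 10% to 50% missing and adjusted correlation 0.5 to 0.8. Both inputs are assumptions. Using Day 29 also removes any bias that runs through Day 29 response, but only reduces bias that comes from the unobserved late titre.

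Three stronger readings are not supported:

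- A reader might infer that the ANCOVA misses a hypothetical estimand already set for revaccinated participants. Table 2 does not list revaccination after Day 29 as an event, its strategy is described as excluding data after the event, and its note treats missing results as missing data. The gap is that late revaccination has no stated handling.
- A reader might infer that every PPS participant has a Day 29 titre for every strain. The rule requires results only for at least one item, so nearly all is the most that can be said.
- A reader might infer that the late ratios are biased. The large shifts in Step 4 need selection on Day 29 titre in one group only, for which the documents give no evidence.

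No power or type I error figure changes, and the Day 29 co-primary analysis is unaffected.

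**What to change.** In SAP 4.3.1, for Day 92 and Day 183 GMT, GMI and GMT ratios, specify a likelihood repeated-measures model on log10 titre at Days 29, 92 and 183. Include group, pre-dose titre, age, country and vaccination history, each by visit, with an unstructured covariance matrix. Keep the planned per-visit ANCOVA as the sensitivity analysis, and keep the Day 29 co-primary ANCOVA as the only reported Day 29 estimate.

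In SAP Table 2, name flu revaccination after Day 29 as an intercurrent event for the secondary estimand, with a hypothetical strategy. Report the observed number per visit and group beside each late estimate.

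The cost is SAP wording, modest programming, and one more model per strain and assay; no new data are needed. The model relies on data being missing at random given Day 29 and the covariates, and it does not cover Day 183 SPR.
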